13.75% to 91.5%, which is at a high level. Symptom distress is negatively correlated with the quality of life of MHD patients. Excessive symptom distress increases the cost of treatment and exacerbates the psychological burden on patients. Persistent symptom burden can significantly affect the quality of life of MHD patients and increase their mortality rate. MHD patients suffer from multiple symptoms at the same time. Li Jiuhong et al.'s research results show that MHD patients experience a total of 3-25 (13.12 ± 5.27) symptoms, which is similar to Weisbord et al.'s average of 9 symptoms. MHD patients experience a wide variety of symptoms, and how to accurately and effectively manage symptoms is the future research direction.

With the prolongation of dialysis treatment time for patients, some urea toxin that cannot be completely cleared by dialysis accumulates in the patient's body, which is closely related to discomfort symptoms such as itching, joint pain, and difficulty falling asleep. Ran Yuli et al. found that the dialysis age of MHD patients is negatively correlated with their physical function and role. With the prolongation of dialysis age, the physiological function of MHD patients will decrease to varying degrees, and various disease-related complications will also occur. The focus of symptom management will shift accordingly. Conducting grouping studies based on dialysis age for MHD patients has certain clinical significance. At present, domestic scholars use a 5-year hemodialysis period as the boundary, dividing dialysis age >5 years into long dialysis age, and dialysis age ≤ 5 years into short dialysis age. Hu Qian and others set up symptom management consultants to develop symptom management pathways and guide responsible nurses to implement symptom management for patients according to the pathway table. The results indicate that setting up symptom management consultants can reduce the incidence of symptoms in MHD patients, improve their quality of life, and improve patient satisfaction. A meta-analysis showed that aerobic exercise can improve several symptoms related to hemodialysis in adults receiving MHD, including restless leg syndrome, depressive symptoms, muscle spasms, and fatigue. Zhao Ying et al. used air wave pressure therapy to prevent dialysis related muscle spasms, Zuo et al. managed symptoms of fatigue through nurse led non drug multidisciplinary holistic care, Beerappa et al. improved sleep

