management measures for depression in clinical practice. Han et al. constructed symptom networks for autism and schizophrenia. Yang Hongli et al. applied symptom networks to HIV infected individuals and identified fatigue as the core symptom. They suggested that when HIV infected individuals have multiple symptoms at the same time, high-intensity and precise intervention on fatigue can reduce the transmission of fatigue as a mediating bridge in the symptom network, reduce the severity of fatigue symptoms, and also alleviate the severity of other symptoms. As mentioned above, symptom network analysis can identify core symptoms, and changing these core symptoms may be an important entry point for changing the entire network. In practical clinical work, implementing key interventions by nurses on core symptoms can more effectively improve other related symptoms and improve intervention efficiency. Applying symptom networks to the field of symptom management is a promising and precise technology in real-world clinical settings.

This study has developed a symptom distress questionnaire for maintenance hemodialysis patients. Previous literature on symptom distress and symptom management in MHD patients has been reviewed. Whether there are differences in symptom distress among MHD patients of different dialysis ages, and how to identify the core symptoms of MHD patients of different dialysis ages through symptom networks to improve the accuracy and effectiveness of intervention are all directions that need to be studied in the future. The research hypotheses of this study are: ① There are differences in the frequency, severity, and degree of symptom distress between long and short dialysis age MHD patients; ② By using network analysis methods to construct symptom networks for long and short dialysis age MHD patients, identify the core symptoms of different dialysis age MHD patients. Based on literature review and clinical experience, it is assumed that the core symptoms of long dialysis age MHD patients are itching or dry skin, while the core symptoms of short dialysis age MHD patients are fatigue or dry mouth.

Contents

1. Current survey of symptom burden in maintenance hemodialysis patients

① Understanding the current status of symptom distress in maintenance hemodialysis patients through cross-sectional questionnaire survey

② Comparative analysis of symptom distress in maintenance hemodialysis patients with long and short dialysis age

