2. Construction of symptom network and core symptom recognition for maintenance hemodialysis patients

① A multicenter study on the current status of symptom distress in maintenance hemodialysis patients

② Construct symptom networks for long-term, short-term, and all maintenance hemodialysis patients using network analysis based on cross-sectional survey data from multiple centers

③ Identify and analyze the core symptoms of long dialysis age, short dialysis age, and all maintenance hemodialysis patients based on network centrality parameters

Methods

Participants

Convenient sampling method was used to select MHD patients from six blood purification centers, including the East, West, South, Baoshan Branch, Ningbo Hangzhou Bay Branch, and Punan Hospital of Renji Hospital Affiliated to Shanghai Jiao Tong University School of Medicine.

(1) Inclusion criteria: ① Age not less than 18 years old; ② Regular hemodialysis time greater than or equal to 3 months; ③ The dialysis plan did not change within one month; ④ Informed consent and voluntary participation in this study.

(2) Exclusion criteria: ① Previous or current mental illness; ② Cognitive impairment; ③ Acute cardiovascular and cerebrovascular disease; ④ Acute infection period; ⑤ Complications such as severe cerebrovascular sequelae and tumors.

(3) Sample size and calculation method: The Dialysis Frequency, Severity, and Symptom Burden Index for dialysis patients used in this study includes a total of 30 symptoms. When constructing a symptom network model, the threshold parameters

that need to be estimated are 30, paired association parameters are $30 \times \frac{(30-1)}{2} = 435$, and the total parameters are $30 + 435 = 465$. Therefore, the sample size needs to be at least 465. Considering 10% of invalid samples, the sample size of this study is at least $465 \div (1 - 10\%) = 517$.

Instruments

General Information Questionnaire: Designed by the researchers themselves, including laboratory examination indicators such as gender, age, dialysis age, marital status, educational level, work status, residential status, medical expense payment method, economic burden, primary disease, comorbidities, recent medication, hemoglobin, etc.

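### With raw-score correlations, node strength partly reflects item variance, so a prevalence difference between dialysis-age groups can look like a different core symptom

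*Combined protocol and SAP*

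**What the plan says.** Methods, Participants, (3) Sample size and calculation method, says: "The Dialysis Frequency, Severity, and Symptom Burden Index for dialysis patients used in this study includes a total of 30 symptoms". The threshold parameters "that need to be estimated are 30", and 435 pairs are added. No symptom is dropped or merged, and no minimum or maximum prevalence is set.

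Contents, item 2, plans to "Construct symptom networks for long-term, short-term, and all maintenance hemodialysis patients using network analysis" and to read core symptoms in each from centrality. The Objective adds that the two groups will be compared. At the end of Background, the first hypothesis expects frequency, severity and distress to differ by dialysis age. The second is to "identify the core symptoms of different dialysis age MHD patients", and expects itching or dry skin in the long group and fatigue or dry mouth in the short group.

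Instruments describes four possible scores per symptom: presence (yes/no), frequency and severity (1-4 each), and distress (0-4). It does not say which one forms the node. It gives no explicit score for an absent symptom, although a total range starting at 0 is reachable only if absence scores 0 on frequency and severity.

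The Statistical Analysis Plan names the qgraph package and three centrality indices, and interprets strength as a symptom's power to influence other symptoms. It states no correlation type, estimator, regularisation, stability check or formal comparison of networks.

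**The concern.** Strength is a sum of edge weights, and an edge built from raw scores depends on how the two items are distributed as well as on how they are related. An item that most patients lack is mostly zeros. A yes/no item that nearly everyone has is mostly ones. In both cases its observed correlations are held down even if its underlying links are as strong as those of any other symptom.

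The first hypothesis predicts that item distributions differ between the groups. If it is true, the same difference can reappear as support for the second hypothesis, with no change in how symptoms relate to one another. The stated product is an intervention target for nurses, chosen because acting on it should relieve other symptoms. A target that only reflects prevalence would not carry that meaning, and a frequency table would already have shown it.

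**Working it through.** **The plan's own figure.** With k = 30, parameters = k + k(k-1)/2 = 30 + 435 = 465, matching "Therefore, the sample size needs to be at least 465". With the 10% allowance, 465 / 0.9 = 516.7, rounded up to 517. Both reproduce, and both confirm that all 30 symptoms are nodes.

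**Group sizes (assumption).** No target per group is given. If the national 31.5% with dialysis age above 5 years (Background) applied, the long group would be 0.315 × 465 = 146 to 0.315 × 517 = 163, and the short group up to 517 - 163 = 354.

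**Why variance matters for yes/no nodes.** All prevalences here are assumed.
- Item variance p(1-p): 0.1375 × 0.8625 = 0.119; 0.50 × 0.50 = 0.250; 0.915 × 0.085 = 0.078.
- The largest possible correlation of two yes/no items with p1 < p2 is √[p1(1-p2) / (p2(1-p1))]. For 13.75% with 50% it is √(0.06875/0.43125) = 0.40. For 50% with 91.5% it is √(0.0425/0.4575) = 0.30. Two 50% items can reach 1.

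**Large-sample simulation.** Thirty nodes had identical latent links (equicorrelation 0.3, or four equal edges each) and differed only in prevalence (5-80% or 13.75-91.5%). Edges were Pearson partial correlations.
- Graded 0-4, absent = 0: mean strength 0.62-0.74 for the five rarest and 0.92-0.97 for the five commonest. Rank correlation of strength with prevalence 0.87-0.99.
- Yes/no: rank correlation with prevalence only -0.14 to 0.34, but 0.89-0.99 with p(1-p). In the sparse network over 13.75-91.5%, strength was 0.67, 0.84 and 0.64 for rare, middle and common symptoms.
- Latent (polychoric or tetrachoric) scale: strength is equal for all nodes by construction, so the population has no prevalence effect.

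**At study size.** Two equally linked hubs, A and B, stood among 28 weaker symptoms, with strength as the sum of Pearson correlations (25 replicates).
- Graded, A 20% and B 60%, n = 354: A outranked B in 4% of samples.
- Graded, A 60% and B 20%, n = 163: A outranked B in 100%.
- Yes/no, A 60% and B 90%, n = 163: the less common hub A led in 100%. With graded scores the same pair split 52% to 48%.

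Further graded runs at 20% versus 60% put the commoner hub ahead in about 72-95% of samples across correlation, partial-correlation and lasso networks. The partial-correlation end of that range is not secure. On re-checking unregularised partial correlations with absolute strength, the lead was weaker at n = 354 and absent at n = 163.

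**Thin cells.** A symptom at an assumed 10% prevalence has 14.6 to 16.3 carriers in a long group of 146 to 163. Two independent ones co-occur in 0.01 × 146 = 1.5 patients.

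**The case against.** The strongest reply is that the effect comes from the scoring and estimator, not from including 30 items, and the plan leaves both open. Latent correlations are not excluded and would remove the effect in the population. This is right, and it limits the point. It does not answer it, because nothing in the SAP commits to such a method.

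A reader might infer that strength simply tracks how common a symptom is. The documents do not support that. Counting one threshold per symptom suggests yes/no nodes, for which very common symptoms also lose strength.

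A reader might also expect large, predictable rank shifts. These do not appear at study size with unregularised partial correlations. Moving one of 30 equally linked graded symptoms from 30% to 60% changed its mean rank from 14.1 to 15.8 at n = 146 and left it at 15.2 at n = 354, with a rank SD of 8-9. Across all nodes, the correlation of strength with prevalence was -0.16 to 0.21 under that estimator, mostly noise. That weakens the prevalence argument there, but a ranking dominated by noise gives no better basis for comparing core symptoms.

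Background's range, "13.75% to 91.5%, which is at a high level", is incidence of symptom distress across studies. It is not a span of item prevalences, and is used above only as an assumed range.

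A prevalence floor required in both groups would be a poor main remedy. It would remove symptoms characteristic of one group, which is the contrast the second hypothesis seeks, and would leave near-universal items untouched. Finally, only strength was examined; closeness and mediation centrality were not.

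**Conclusion.** The point holds in a limited form. All 30 symptoms enter each network without a rule for rare or near-universal items, core symptoms are compared by centrality alone, and the groups are expected to differ in symptom frequency. With raw-score correlations, a prevalence difference can by itself change which of two equally linked symptoms leads. The direction depends on the score: upward with prevalence for graded scores with absent = 0, and towards mid-range prevalence for yes/no nodes.

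The size in this study cannot be computed. The documents give no item prevalence by group, and do not state the node score or estimator. The simulated figures rest on assumed prevalences, equal latent links and, for group size, the national 31.5%. They show that the mechanism exists and do not estimate the bias. It would go too far to infer that the core symptoms found here will be artefacts of prevalence. This is worth correcting in the SAP and does not invalidate the design.

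**What to change.** In the Statistical Analysis Plan:

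1. Use the same node set and the same named node score, with an absent symptom coded 0, in all three networks. State the correlation type and estimator.
2. For each group, report every symptom's prevalence and SD beside its strength, with the correlation of strength and SD across symptoms. Show the correlation with prevalence as well, because for graded scores the link with SD depends on how the grades are spaced.
3. State that a between-group difference in core symptom will not be read as a difference in how symptoms relate, or in their power to influence others, when it coincides with a difference in that symptom's prevalence or SD. Flag such differences; do not suppress them.
4. Add a sensitivity network from polychoric or tetrachoric correlations, with smoothing or regularisation specified. Simulated tetrachoric matrices at n = 146 were not positive definite in any run (30 of 30 in one set, 6 of 6 in another).
5. Add a sensitivity network that leaves out very rare and near-universal items, with the cut-offs fixed before the data are examined.

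No new data are needed. The cost is some SAP wording, a little more analysis and a more cautious between-group conclusion.

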Study Protocol and Statistical Analysis Plan

(Version: 2.0 Date: 2023.3.28)

Name: Construction of Symptom Network in Maintenance Hemodialysis Patients

Applicant: Ren Ji Hospital, Shanghai Jiao Tong University School of Medicine

Principal investigator: [name]

Objective

Through a cross-sectional questionnaire survey, a general information questionnaire and Dialysis Frequency, Severity, and Symptom Burden Index were used to investigate the frequency, severity, and degree of symptom distress in MHD patients, and to analyze the differences in symptom distress status between long and short dialysis age MHD patients. Using the R 4.2.2 software qgraph package, construct symptom networks for MHD patients of long and short dialysis age through network analysis. Analyze network centrality indicators, including intensity, closeness centrality, and mediation centrality, to identify core symptoms and compare if there are any differences between the two groups, aiming to lay the foundation for precise and efficient phased symptom management.

Background

End stage renal disease (ESRD) is caused by various kidney diseases, leading to irreversible decline in renal function. The main renal replacement therapy (RRT) for ESRD is hemodialysis (HD), peritoneal dialysis (PD), and kidney transplantation. Due to the impact of kidney supply on kidney transplantation, it is limited in clinical practice, and hemodialysis has become the most common method of RRT in most countries. According to the registration system of the Chinese Research Data Services (CNRDS), as of the end of 2021, there were 751098 dialysis patients and 155738 new patients in China, with an average dialysis age of 50.9 months. The proportion of patients with dialysis age greater than 5 years was 31.5%. There are a large number of hemodialysis patients with a longer dialysis age.

With the continuous development of dialysis technology, the survival rate of maintenance hemodialysis (MHD) patients is becoming higher and higher. However, MHD patients may experience various symptoms during long-term treatment, which is the main cause of discomfort and physical and mental health for patients. The physical and mental pain or torment experienced by patients due to the disease itself and/or the symptoms caused by treatment is called symptom distress. Multiple studies have shown that the incidence of symptom distress in MHD patients ranges from

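### The minimum of 465 valid patients (517 enrolled) covers one 30-symptom network, but two more are planned in disjoint dialysis-age groups that cannot both meet the same rule at that size

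*Combined protocol and SAP*

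**What the plan says.** Under Methods, Participants, (3) Sample size and calculation method, the plan notes that the symptom index "used in this study includes a total of 30 symptoms". It counts 30 threshold parameters and 435 pairwise parameters and states "Therefore, the sample size needs to be at least 465". One allowance for 10% invalid samples raises this to a study minimum of 517. The paragraph does not mention dialysis-age groups.

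Elsewhere the plan asks for more than one network:

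- The Objective sets out to "construct symptom networks for MHD patients of long and short dialysis age through network analysis", and to use centrality "to identify core symptoms and compare if there are any differences between the two groups".
- Contents item 2 lists three networks: "Construct symptom networks for long-term, short-term, and all maintenance hemodialysis patients using network analysis".
- Research hypothesis 2 (end of Background) expects the core symptoms to differ. For the long group, "it is assumed that the core symptoms of long dialysis age MHD patients are itching or dry skin"; for the short group, fatigue or dry mouth.

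The only definition of the groups is in the Background, which reports the practice of "dividing dialysis age >5 years into long dialysis age, and dialysis age ≤ 5 years into short dialysis age". Recruitment is by convenience sampling at six centres, with no quota or minimum for either group.

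**The concern.** The plan has one sample-size criterion, at least one valid patient per network parameter, and applies it once, to all patients together. The networks named in the Objective and in hypothesis 2 are the two group networks. The all-patient network, the only one the calculation covers, appears in Contents item 2 but in neither of those places.

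A study that stopped at its stated minimum could therefore report core symptoms for each group, and a difference between groups, from networks that fall short of the plan's own standard. A reader of the sample-size paragraph would not learn this. The Objective intends the results to support symptom management by phase of dialysis, so the group-specific findings are the ones meant to be used.

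**Working it through.** **Inputs.** Symptoms p = 30, the one-per-parameter rule and the 10% invalid allowance come from the sample-size paragraph. The division at 5 years comes from the Background. The study's own split between groups is not given, so it is varied below as an assumption. One value is the national figure in the Background: "The proportion of patients with dialysis age greater than 5 years was 31.5" per cent. It describes dialysis patients nationally, whereas this is a convenience sample from six centres, so it only illustrates.

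**Step 1: reproduce the plan's figure.** Parameters per network = p + p(p − 1)/2 = 30 + 30 × 29/2 = 30 + 435 = 465. Enrolment = 465/(1 − 0.10) = 516.7, rounded up to 517. Both figures reproduce for one network.

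**Step 2: apply the same rule to both groups.** No reduced symptom set is planned, so each group network has 465 parameters. The groups are disjoint, so 2 × 465 = 930 valid patients are needed. Enrolment = 930/0.90 = 1,033.3, rounded up to 1,034, or 517 per group.

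**Step 3: what the stated minimum can give.**

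- With 465 valid patients, the smaller group has at most 232 (465/2 = 232.5, rounded down). 232/465 = 0.50 patients per parameter. Neither group reaches 465 unless the other is empty.
- If all 517 enrolled were valid, the smaller group has at most 258 (517/2 = 258.5, rounded down). One group could reach 465 only if the other had no more than 517 − 465 = 52 patients.

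**Step 4: range by assumed share s with long dialysis age.** Group sizes are 465 × s and 465 × (1 − s). The total valid needed without quotas is 465/min(s, 1 − s), rounded up. Enrolment is that total divided by 0.90, rounded up.

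| Assumed s | Long / short among 465 valid | Patients per parameter | Total valid for both to reach 465 | Enrolled |
|---|---|---|---|---|
| 20% | 93 / 372 | 0.20 / 0.80 | 2,325 | 2,584 |
| 31.5% | 146 / 319 | 0.31 / 0.69 | 1,477 | 1,642 |
| 40% | 186 / 279 | 0.40 / 0.60 | 1,163 | 1,293 |
| 50% | 232 / 233 | 0.50 / 0.50 | 930 | 1,034 |

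The totals in the first three rows assume unrestricted recruitment at that share, and they give 465 in the smaller group only on average. With quotas of 517 enrolled per group, 1,034 is enough whatever the population share, given the plan's 10% allowance.

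**The case against.** The strongest reply is that one patient per parameter is a rule of thumb for which the plan gives no source. Falling below it does not show that centrality estimates would be unstable. This stands: the check tests the plan against its own rule and does not show how a network from 232 patients would perform. The documents do not let anyone judge that either. The Statistical Analysis Plan names the qgraph package and three centrality indices, but no estimator, regularisation, stability check or formal comparison of networks. For the same reason, nothing in the plan justifies a smaller group size. If the rule was meant only for the pooled network, the group networks have no sample-size justification at all.

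A second reply is that 465 and 517 are floors and more patients may be enrolled. That also stands, and the conclusion is limited to the stated minimum. A floor is nevertheless the plan's statement of what is enough, and this one is not enough for the group networks by the plan's own count. It does follow that an exploratory label should depend on the group sizes actually reached.

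Third, the 5-year boundary is reported in the Background as existing practice and is not restated in Methods. This does not matter to the conclusion, since any single cut-off gives disjoint groups. Only the 31.5% illustration depends on it.

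**Conclusion.** The concern holds. The arithmetic behind 465 and 517 is correct, but its scope is one network. At the stated minimum the two group networks cannot both meet the one-per-parameter rule: 930 valid patients are needed, against 465 planned as valid, or 517 if none were invalid. At 465 valid, both networks fall short whenever both groups contain patients. The smaller has at most 0.50 patients per parameter, and 0.20 to 0.40 at assumed shares of 20% to 40%.

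The conclusion rests on the plan's own rule, its full set of 30 symptoms in each network, and disjoint groups. It does not rest on any assumed split. Because it affects analyses named in the Objective and in hypothesis 2, and concerns the only sample-size argument in the plan, it must be corrected.

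**What to change.** Restate the sample-size paragraph so that it says:

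1. 465 valid (517 enrolled) satisfies the one-per-parameter rule for the all-patient network only.
2. The expected valid sizes of the long and short groups, as a range by split (for example 93/372 at 20% to 232/233 at 50%), with every share labelled as an assumption.
3. At this size the group networks do not both meet the rule, and the smaller group has at most 232 valid patients.

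Then label the group-specific core symptoms and their comparison exploratory unless each group reaches 465 valid patients. This rewords one paragraph, adds a label and enrols no one. The cost is a less favourable statement of adequacy and weaker wording for the comparison.

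If the sponsor wants the group results to carry more weight, there are three routes, each costing more than rewording:

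- Set a minimum of 465 valid (517 enrolled) per group with quotas, 1,034 enrolled in all.
- Justify a smaller group size by simulation or a pre-specified stability criterion.
- Reduce the number of symptoms. By the plan's count, p(p + 1)/2, a group of 232 supports at most 21 symptoms (231 parameters), 146 supports 16 (136) and 93 supports 13 (91). The reduced set should be pre-specified and identical in both groups so that centrality stays comparable. It should keep itching, dry skin, fatigue and dry mouth, without which hypothesis 2 could not be examined.

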Enter the collected information into the database established by Epidata 3.1, and after verification, import it into SPSS 21.0 software for data analysis. The patient's gender, marital status, education level, work status, and other counting data are described using frequency and percentage. Age, hemoglobin, blood phosphorus, and other measuring data that meet normality are represented by mean and standard deviation, while those that do not meet normality are represented by median and interquartile spacing. The symptom distress scores of MHD patients with different characteristics were tested for normality and homogeneity of variance. If they obey the normal distribution and have the same variance, t-test and analysis of variance were used. Otherwise, nonparametric rank sum test was used. Use R4.2.2 software qgraph package for network analysis to generate complex network descriptions of the relationship between symptoms. Use network centrality indicators such as strength, tight centrality, and mediation centrality to represent the degree of interconnection of symptom networks. The intensity reflects the total direct connection between symptoms and other symptoms, that is, the ability of symptoms to affect other symptoms; The closeness centrality reflects the reciprocal of the distance between symptoms and other symptoms, that is, the core position of symptoms in the network; Mediation centrality reflects the number of shortest paths through the symptom, which serves as a bridge between the symptoms in the network.

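### Normal scores that fail the equal-variance check are sent to the rank-sum test, which itself assumes equal spread; Welch's test would hold the 5% level

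*Combined protocol and SAP*

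**What the plan says.** The Statistical Analysis Plan section states: "The symptom distress scores of MHD patients with different characteristics were tested for normality and homogeneity of variance". If the scores are normal and "have the same variance, t-test and analysis of variance were used. Otherwise, nonparametric rank sum test was used". The parametric test is used only when both checks pass, so a score that passes normality and fails equal variance goes to the rank-sum test. No unequal-variance test is named anywhere. The document gives no significance level, no score SD, and no statement of what the rank-sum result is to be read as.

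The same section summarises normally distributed measurements by mean and SD, and others by median and interquartile range.

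The comparison of main interest is hypothesis 1 at the end of the Background: "There are differences in the frequency, severity, and degree of symptom distress between long and short dialysis age MHD patients". The groups are formed by "dividing dialysis age >5 years into long dialysis age, and dialysis age ≤ 5 years into short dialysis age". Their sizes are not fixed by design. Under Participants, "Convenient sampling method was used to select MHD patients from six blood purification centers", with no quota by dialysis age. The only figure for the split is national, in the Background: "The proportion of patients with dialysis age greater than 5 years was 31.5" per cent.

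**The concern.** The rank-sum test is valid for the null hypothesis that the two distributions are identical, and that includes equal spread. The plan sends a score to it because the spreads were found to differ, so the reason for the switch contradicts what the test assumes. With unequal spreads it is not a valid 5% test of equal means. Nor is it a valid 5% test that each group is equally likely to score higher, because its usual variance is wrong for that null too.

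This is the plan's only stated rule for testing scores between groups. If the branch is reached with uneven groups, the p-value is somewhat too small when the smaller group is the more variable and somewhat too large when the larger group is. If the scores follow the plan's descriptive rule, such a result would also sit beside means and SDs that it does not test.

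**Working it through.** **The plan's own figure.** Participants, item (3): 30 thresholds + 30 × 29 / 2 = 435 pairwise parameters gives 465 ("Therefore, the sample size needs to be at least 465"). Then 465 / 0.9 = 516.7, rounded up to 517 ("Considering 10% of invalid samples, the sample size of this study is at least" 517). Both reproduce. Neither depends on the present point; 465 is used below as the evaluable number.

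**Assumptions.** Normal scores, equal means, two-sided 5%. Long share 31.5%: 0.315 × 465 = 146 long, leaving 319 short. SD ratios k = long/short from 0.5 to 2, since the document gives none.

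**Formula.** Let n1 = 146 (SD k), n2 = 319 (SD 1), r1 = k²/(k² + 1) and r2 = 1/(k² + 1). The true variance of the rank-sum statistic U, divided by n1·n2, is

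0.25 + (n2 − 1)·asin(r1)/(2π) + (n1 − 1)·asin(r2)/(2π).

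The test uses (n1 + n2 + 1)/12 = 466/12 = 38.83 instead. The actual rejection rate is 2·[1 − Φ(1.96·√(38.83/true))].

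- k = 2: r1 = 0.8, r2 = 0.2. True = 0.25 + 318 × 0.1476 + 145 × 0.0320 = 51.8. 1.96 × √(38.83/51.8) = 1.70, so the rate is 9.0%.
- k = 1.25: r1 = 0.610, r2 = 0.390. True = 0.25 + 318 × 0.1044 + 145 × 0.0638 = 42.7. 1.96 × √(38.83/42.7) = 1.87, so the rate is 6.2%.
- k = 0.5: r1 = 0.2, r2 = 0.8. True = 0.25 + 318 × 0.0320 + 145 × 0.1476 = 31.8. 1.96 × √(38.83/31.8) = 2.16, so the rate is 3.0%.

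**Simulation**, 146 vs 319, 20,000 runs per cell (standard error about 0.15 points, 0.2 at the highest rates):

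| SD ratio long/short | 0.5 | 0.8 | 1 | 1.25 | 1.5 | 2 |
|---|---|---|---|---|---|---|
| Rank-sum, formula | 3.0% | 4.1% | 5.0% | 6.2% | 7.2% | 9.0% |
| Rank-sum, simulated | 3.0% | 4.4% | 5.0% | 6.2% | 7.2% | 9.0% |
| Pooled t, simulated | 1.3% | 3.7% | 4.9% | 7.1% | 8.9% | 11.9% |

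At ratio 0.8, repeat simulations gave 3.8% to 4.4%, around the formula's 4.1%. Welch's t-test gave 4.7% to 5.3% at every ratio and at every split tried.

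**Other splits**, rank-sum, simulated:

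| Long vs short | Ratios 0.5 to 2 | Ratios 0.8 to 1.25 |
|---|---|---|
| 186 vs 279 | 4.4–7.7% | 4.5–5.3% |
| 209 vs 256 | 4.9–6.7% | 4.9–5.2% |
| 232 vs 233 | 4.9–6.1% | 4.9–5.3% |

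**The whole rule.** The plan does not name its checks, so Shapiro-Wilk in each group and then Levene were assumed, each at 5%. At 146 vs 319:

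| SD ratio | 0.5 | 0.8 | 1.25 | 2 |
|---|---|---|---|---|
| Branch reached | 90% | 75% | 76% | 90% |
| Current rule rejects | 3.0% | 4.2% | 6.4% | 9.0% |
| Welch if normal, else rank-sum | 4.9% | 5.0% | 5.4% | 5.6% |

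The ceiling of 90% is 0.95 × 0.95, the chance that both groups pass normality.

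**When scores are skewed** (gamma scores, SD ratio 1.25, same split, 2,000 runs), the branch is reached in 52%, 31%, 9%, 0.2% and 0% of runs as the short group's coefficient of variation rises through 0.10, 0.15, 0.20, 0.30 and 0.40.

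**Three groups** (assumed 65/140/260, rank test taken as Kruskal-Wallis): 6.0%, 7.1% and 8.9% when the smallest group's SD is 1.25, 1.5 and 2 times the others, and 3.1% at 0.5 times. Equal thirds give 4.9% to 5.8%. Welch ANOVA gives 4.6% to 5.3% throughout.

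**The case against.** **The reading is not stated.** Nothing says the rank-sum result will be taken as a mean difference. Hypothesis 1 speaks only of differences and fits the null of identical distributions, under which unequal spread is itself a true difference. The mean-and-SD sentence names laboratory and demographic measurements and may not cover the scores. This stands in part. It protects only the bare distributional reading. In the simulations each group is equally likely to score higher, so the same error rates apply to that reading as well.

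**The branch may rarely be reached.** The 75% to 90% figures assume exactly normal scores. The instrument is a bounded sum of Likert items (0 to 360), and single-item scores will hardly pass a normality test at this sample size. The nearest dispersion in the document is a cited study's symptom count, 13.12 ± 5.27, a coefficient of variation of 5.27/13.12 = 0.40; at 0.40 the gamma check reaches the branch in 0% of runs. That figure is for a count and not for this score, and gamma is one shape among several. A rough model built from that count and assumed Likert items (300 runs) reached the branch in 63%, 17% and 0% of runs as the assumed between-patient severity SD rose through 0, 0.3 and 0.6. Reach is unknown and could be nil. This stands.

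**The size is small where it is plausible.** About one point at ratios of 0.8 to 1.25, and less in near-equal groups. The 9.0% needs a twofold SD ratio, which nothing in the document supports, and a national split. This stands.

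**The fallback is conventional and partly protective.** In uneven groups the rank-sum test is nearer 5% than the pooled t-test. That is true, and it is why the remedy is not to drop the variance check and keep the pooled test. Nor is the lack of an effect estimate peculiar to this branch: the plan specifies no estimate or confidence interval for any test.

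**Conclusion.** The concern holds, as a minor point. This is a flaw in a stated rule rather than a missing detail: normal scores with unequal variances are routed to a test whose null variance assumes equal spread. At 146 vs 319 and nominal 5%, the rank-sum rate is about 4% to 6% at SD ratios of 0.8 to 1.25. The wider range of 3.0% to 9.0% arises only at ratios of 0.5 to 2. Welch's test stays within 4.7% to 5.3%.

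This rests on normal scores, an assumed level, assumed SD ratios and a national split. It matters only if a score passes normality, fails equal variance, and is compared between uneven groups. Use of the rank-sum test for clearly non-normal scores is not criticised. Confidence is medium, because how often the branch is reached cannot be judged from the document.

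**What to change.** Remove unequal variance as a trigger for the rank-sum test and leave the rest of the rule. Suggested text:

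> Approximately normal scores are compared with Welch's t-test (Welch ANOVA for more than two groups), whatever the variance check shows, and reported as the mean difference with 95% CI. Clearly non-normal scores are compared with the rank-sum test, read as a difference in distribution (the probability that one group scores higher) and not as a difference in means or medians.

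If non-normal scores also differ in spread, the Brunner-Munzel test is an option.

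The cost is one sentence, and Welch's tests are standard SPSS output. With equal SDs and a shift of 0.3 SD, simulated power is 85.0% (Welch) vs 85.2% (pooled t) at 146 vs 319, and 89.3% for both at 232 vs 233. Against the rank-sum test at 146 vs 319, Welch has 93.1% vs 90.6% at SD ratio 0.8, and 72.5% vs 72.9% at 1.25, where the rank-sum test already rejects 6.2% with no difference in means. Skewed scores keep their present test and power, and the sample size is unaffected.
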